7.1 Adverse Events

The investigator shall truthfully fill in the Adverse Event Record Form, record the occurrence time, severity, duration, measures taken and outcome of the adverse event, and explain the criteria for judging the severity of the adverse event and the five-level classification criteria for judging the relationship between the adverse event and the test drug (definitely related, possibly related, possibly unrelated, unrelated and unable to determine). All adverse events should be followed up until they are resolved or stable.

Preventive measures for adverse events:

- ① Ultrasound-guided nerve block can visualize the puncture needle tip, effectively and greatly reduce the risk of local anesthetic poisoning and the damage caused by the puncture.
- ② Poisoning of local anesthetics: strict control of drug dosage and close intraoperative monitoring. Once it occurs, it should be treated immediately according to the treatment process of local anesthetic poisoning, such as ECG monitoring, respiratory tract management, volume control, the use of sedative anticonvulsant and corresponding vasoactive drugs.
- ③ Puncture injury: Ultrasound visualization and careful operation to ensure that tissue damage is minimized. Once it occurs, surgical intervention can be carried out

according to the severity.

Physicians will do their best to prevent and treat injuries that may result from this study. If an adverse event occurs in a clinical trial, a committee of medical experts will determine whether it is related to the intervention. The sponsor will provide the cost of treatment and corresponding economic compensation for the damage related to the test in accordance with the provisions of Good Clinical Practice (GCP) .

7.2 Serious Adverse Events

Serious adverse events were defined as adverse events that resulted in one of the following outcomes: death, prolonged hospitalization, disability, fatal reaction, or teratogenicity. Any serious adverse event occurring during the clinical trial must be reported to the principal investigator of the Department of Anesthesiology of Tongji Hospital and the Ethics Committee of the Drug Clinical Research Base of Tongji Hospital within 24 hours.

7.3 Safety monitoring

The data security management committee is composed of anesthesiologists. An interim analysis was conducted by the committee when half of the patients were enrolled. The study was discontinued if the interim analysis revealed a significant increase in mortality rate in the test group, or if there were significantly more complications.

8 Matters of Medical Ethics

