3.2 Sample size estimation

According to an preliminary experiment (7 patients in the serratus anterior plane block combined with erector spinae plane block group and 7 patients in the thoracic paravertebral block group), the results showed that the 24h postoperative morphine consumption was 23.7 ± 4.8 mg in the SAPB & ESPB group and 28.7 ± 4.2 mg in the PVB group. A difference of 2.5 mg in the 24h postoperative morphine consumption was chosen as the minimum expected difference between the two groups. 1:1 enrollment would require 41 patients in each group to achieve a significance level of 0.05 for a one-sided test and performance test of 80%. A total sample size of 92 subjects was required if the dropout rate was set at 10%.

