9.3 Reasons for dropout

For any dropout case, the investigator must record the reasons for the dropout. In general, there are five reasons, namely, adverse events, violation of the trial protocol, loss to follow-up (including self-withdrawal of the subject), discontinuation of the sponsor and others.

10. Statistical analysis

Measurement data were analyzed and compared by t-test or Mann-Whitney U test, depending on whether the data were distributed normally or not. Repeated measures data (e.g., morphine consumption, VAS scores, pulmonary function measures) were analyzed using one-way analysis of variance(ANOVA). Enumeration data were compared by χ^2 or Fisher's exact test. $p < 0.05$ was considered significant.

11. Summary of lab report

Unblinding is performed when the statistical analysis is completed and the statistical analysis report is written by the statistical analyst. The statistical analysis report after Unblinding shall be delivered to the main researchers of the experiment to write the research report.

12 Data preservation

The research data related to this clinical trial were kept by the Department of Anesthesiology of Tongji Hospital.

References:

1. Bendixen, M., et al., *Postoperative pain and quality of life after lobectomy via video-assisted thoracoscopic surgery or anterolateral thoracotomy for early stage lung cancer: a randomised controlled trial*. Lancet Oncol, 2016. 17(6): p. 836-844.
2. Kaplowitz, J. and P.J. Papadakos, *Acute pain management for video-assisted thoracoscopic surgery: an update*. J Cardiothorac Vasc Anesth, 2012. 26(2): p. 312-21.
3. Elmore, B., et al., *Pain Management Following Thoracic Surgery*. Thorac Surg Clin, 2015. 25(4): p. 393-409.
4. Kumar, K., et al., *A Review of Opioid-Sparing Modalities in Perioperative Pain Management: Methods to Decrease Opioid Use Postoperatively*. Anesth Analg, 2017. 125(5): p. 1749-1760.

5. Joshi, G.P., et al., *A systematic review of randomized trials evaluating regional techniques for postthoracotomy analgesia*. Anesth Analg, 2008. 107(3): p. 1026-40.
6. Zhu, M., et al., *Ultrasound-Guided Intercostal Nerve Block Following Esophagectomy for Acute Postoperative Pain Relief in the Postanesthesia Care Unit*. Pain Pract, 2018. 18(7): p. 879-883.

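### The section 7.3 rule makes stopping for deaths depend on a significant increase at one look at about 23 patients per arm, so it gives almost no protection against deaths

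*Combined protocol and SAP*

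**What the plan says.** The combined protocol and SAP puts its trial-level harm rule in section 7.3. The timing is a single look: "An interim analysis was conducted by the committee when half of the patients were enrolled". There are two grounds for stopping. The first is mortality: "The study was discontinued if the interim analysis revealed a significant increase in mortality rate in the test group". The second follows in the same sentence: "or if there were significantly more complications".

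Section 7.3 gives no test, sidedness, interim significance level or event count, and does not say which complications are compared. The only general definition is in section 10, which allows chi-square or Fisher's exact test for counts and says that p below 0.05 "was considered significant", without stating sidedness.

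The size of the look follows from section 3.2: "1:1 enrollment would require 41 patients in each group", and with dropout, "A total sample size of 92 subjects was required if the dropout rate was set at 10" per cent.

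Outside 7.3, section 7.2 requires serious adverse events to go to the principal investigator and the ethics committee within 24 hours. Section 7.1 has a committee of medical experts judge whether an adverse event is related to the intervention. Neither section says what would then happen to the trial.

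**The concern.** A significance test is a poor trigger for a rare and grave event in a small sample. Section 4.1 admits only ASA I-II patients, so few deaths are expected and any would call for scrutiny. At about 23 per arm, an excess must be very large before p falls below 0.05. A committee that followed the written rule could therefore see several deaths in the test arm and none in the control arm without the rule being met. The protocol would then offer patients and the ethics committee a mortality safeguard that its own sample size cannot deliver.

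**Working it through.** **Inputs.** From section 3.2: pilot SDs of 4.8 and 4.2 mg, difference 2.5 mg, one-sided 0.05, power 80%, 1:1 allocation, 10% dropout. From section 7.3: the look at half enrolment. From section 10: p<0.05, chi-square or Fisher. The event rates below are assumptions, because the documents give none.

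**Step 1: the plan's sample size.** Pooled SD = √((4.8² + 4.2²)/2) = √20.34 = 4.51 mg. n per arm = 2 × (1.645 + 0.842)² × 20.34 / 2.5² = 40.3, rounded up to 41. With dropout, 41/0.9 = 45.6, rounded up to 46 per arm, or 92 in total. The stated figures reproduce.

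**Step 2: size of the look.** 92/2 = 46, or about 23 per arm. This is derived, not stated. It assumes balance, and section 3.3 describes no blocking.

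**Step 3: smallest excess that is significant against no control deaths.** For x against 0 at 23 per arm, one-sided Fisher p = C(23,x)/C(46,x), and the two-sided value is twice that. For x=4: 8,855/163,185 = 0.054, doubled 0.109. For x=5: 33,649/1,370,754 = 0.0245, doubled 0.049. Uncorrected chi-square for 4 against 0 is 46 × (4×23)² / (23×23×4×42) = 4.38, p=0.036.

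| Test | 3 v 0 | 4 v 0 | 5 v 0 | 6 v 0 | Smallest excess with p<0.05 |
|---|---|---|---|---|---|
| Fisher, two-sided | 0.233 | 0.109 | 0.049 | 0.022 | 5 v 0 |
| Fisher, one-sided | 0.117 | 0.054 | 0.025 | 0.011 | 5 v 0 |
| Chi-square, uncorrected | 0.073 | 0.036 | 0.018 | 0.009 | 4 v 0 |
| Chi-square, continuity-corrected | 0.232 | 0.116 | 0.058 | 0.029 | 6 v 0 |

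With one control death, two-sided Fisher needs 7 (p=0.047). The thresholds against 0 are the same at 20 or 21 per arm, which would apply if half were counted on the 82 evaluable patients.

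**Step 4: how often the mortality ground would fire.** With no control deaths this is P(X ≥ k), where X is binomial(23, p), with k=5 for Fisher and k=4 for uncorrected chi-square. With a non-zero control rate, the two binomials are summed over all outcomes where the test arm has more deaths and p<0.05.

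| Assumed mortality, test v control | Fisher, two-sided | Chi-square, uncorrected |
|---|---|---|
| 5% v 0% | 0.5% | 2.6% |
| 5% v 1% | 0.4% | 2.1% |
| 10% v 0% | 7.3% | 19.3% |
| 10% v 1% | 5.9% | 15.7% |
| 20% v 0% | 49.9% | 70.4% |

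At 5% mortality the expected number of test-arm deaths is 23 × 0.05 = 1.15, far below any threshold in step 3.

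**Step 5: the complications ground, for contrast.** By the same method, for one comparison with two-sided Fisher and assumed rates, it fires 9% of the time at 20% v 10%, 30% at 30% v 10%, and 57% at 40% v 10%.

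**The case against.** Four points on the other side have force.

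- **The rule has two grounds.** A reader might infer that the whole safeguard would almost never act. The documents do not support that: step 5 shows that the complications ground can act on large excesses. It is weak for moderate ones, and its events are undefined, but it is not inert. Its false-stop rate cannot be calculated either. Treating the reactions listed in section 5 as separately tested complications would invent a procedure that the protocol does not state.
- **The wording gives a sufficient condition.** Section 7.3 says the study stops if the increase is significant, not only if. A reader might infer that 4 deaths against 0 must be ignored and enrolment must go on. The text does not say so, and under uncorrected chi-square 4 against 0 would meet the rule.
- **The 5 against 0 threshold is conditional.** Applying section 10 to section 7.3, and choosing Fisher, are both inferences. They are reasonable ones at such small counts, and the other tests move the threshold only to 4 or 6.
- **Deaths are not hidden until patient 46.** Sections 7.1 and 7.2 provide rapid reporting and a judgement of relatedness, and section 9.3 lists discontinuation by the sponsor among the dropout reasons, so the sponsor's power to stop is at least implied.

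These points limit the scope to deaths and require the test to be named as an assumption. They do not supply what is missing: sections 7.1 and 7.2 do not mention the 7.3 committee, give nobody a stated power to pause, and attach no trial-level action. Section 4.3 withdraws individual patients. Any protection beyond the written rule rests on unwritten discretion.

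**Conclusion.** The concern holds for the mortality ground. At about 23 per arm it needs 5 deaths against 0 by Fisher, 4 by uncorrected chi-square or 6 with continuity correction. At an assumed 5% v 0% mortality it would fire about 0.5% of the time by Fisher and 2.6% by the most lenient test. It reaches about one chance in two by Fisher only at 20% v 0%. The conclusion rests on balanced arms, on section 10's p<0.05 governing section 7.3, and on assumed death rates. The choice of test changes the figures but not the conclusion at 5%. It does not extend to the complications ground, where the defect is that the events, test and level are undefined.

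**What to change.** In section 7.3:

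- Remove statistical significance as the required trigger for deaths.
- Send each death and serious adverse event to the committee as it occurs, with allocation available to the committee only, so that it can recommend a pause or stop on case review. Refer to this route in section 7.2.
- Keep the half-enrolment look as a scheduled review of counts by arm with confidence intervals.
- Leave any threshold to the committee.

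The cost is wording in 7.3 and 7.2 and a short committee procedure. Sample size, treatments and endpoints do not change. There are two downsides. There is a small chance of a precautionary pause for events that prove unrelated. Committee members would also see allocation before the end of the analysis, where section 11 places unblinding, so they should not include the blinded follow-up investigator or the analyst. Section 7.3 says only that members are anesthesiologists, so this separation has to be written in.

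The complications being compared also need to be defined. Restricting them to rare serious events would be a trade-off, since that ground would then act less often.

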8.1 Responsibilities of the investigator

The investigator is responsible for the trial and ensures that the study is conducted in accordance with the study protocol and ethical guidelines at home and abroad. Before the trial, the clinical study protocol and written informed consent were submitted to the Independent Ethics Committee of Drug Clinical Trial of Tongji Hospital of Huazhong University of Science and Technology for review, and the trial could be started only after approval.

8.2 Subject Information and Informed Consent

The investigator shall obtain the written informed consent of the subject before the subject participates in the study. The investigator shall explain the nature, purpose and risks of the clinical trial to the subject, and make sure that the subject has the right to withdraw at any time after agreeing to participate in the trial. After full consideration, the subject voluntarily participated in the clinical trial, and both the subject and the investigator signed and dated the Informed Consent Form.

9. Dropout cases

9.1 Definition of dropout cases

All patients who have filled in the informed consent form and qualified to enter the trial have the right to withdraw from the clinical trial at any time, no matter when and for any reason, as long as the subjects fail to complete the observation cycle

specified in the protocol, they are called dropout cases

9.2 Treatment of dropout cases

Patients drop-out due to adverse reactions which were judged to be relevant for trial intervention after follow-up must be recorded and notified to the sponsor. The dropout due to violation of the test protocol shall be recorded and explained.

9.3 Reasons for dropout

For any dropout case, the investigator must record the reasons for the dropout. In general, there are five reasons, namely, adverse events, violation of the trial protocol, loss to follow-up (including self-withdrawal of the subject), discontinuation of the sponsor and others.

10. Statistical analysis

Measurement data were analyzed and compared by t-test or Mann-Whitney U test, depending on whether the data were distributed normally or not. Repeated measures data (e.g., morphine consumption, VAS scores, pulmonary function measures) were analyzed using one-way analysis of variance(ANOVA). Enumeration data were compared by χ^2 or Fisher's exact test. $p < 0.05$ was considered significant.

11. Summary of lab report

Unblinding is performed when the statistical analysis is completed and the statistical analysis report is written by the statistical analyst. The statistical analysis report after Unblinding shall be delivered to the main researchers of the experiment to write the research report.

12 Data preservation

The research data related to this clinical trial were kept by the Department of Anesthesiology of Tongji Hospital.

References:

1. Bendixen, M., et al., *Postoperative pain and quality of life after lobectomy via video-assisted thoracoscopic surgery or anterolateral thoracotomy for early stage lung cancer: a randomised controlled trial*. Lancet Oncol, 2016. 17(6): p. 836-844.
2. Kaplowitz, J. and P.J. Papadakos, *Acute pain management for video-assisted thoracoscopic surgery: an update*. J Cardiothorac Vasc Anesth, 2012. 26(2): p. 312-21.
3. Elmore, B., et al., *Pain Management Following Thoracic Surgery*. Thorac Surg Clin, 2015. 25(4): p. 393-409.
4. Kumar, K., et al., *A Review of Opioid-Sparing Modalities in Perioperative Pain Management: Methods to Decrease Opioid Use Postoperatively*. Anesth Analg, 2017. 125(5): p. 1749-1760.

5. Joshi, G.P., et al., *A systematic review of randomized trials evaluating regional techniques for postthoracotomy analgesia*. Anesth Analg, 2008. 107(3): p. 1026-40.
6. Zhu, M., et al., *Ultrasound-Guided Intercostal Nerve Block Following Esophagectomy for Acute Postoperative Pain Relief in the Postanesthesia Care Unit*. Pain Pract, 2018. 18(7): p. 879-883.

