- 6) Anesthesia maintenance: 1-2% sevoflurane, dexmedetomidine 0.5 μ g \cdot kg $^{-1}$ \cdot h $^{-1}$ and remifentanil 0.1-0.2 μ g \cdot kg $^{-1}$ \cdot min $^{-1}$. Maintain the stability of intraoperative vital signs. Volume control ventilation mode: tidal volume was 6-8ml/kg, airway pressure was maintained within 25cmH₂O, end-expiratory CO₂ was maintained within 35-45mmHg, and lungs were dilated once every 1 hour. ECG, HR, BP, SpO₂, PetCO₂, body temperature, liquid intake and output were monitored. During the operation, vasoactive drugs were used as needed to maintain blood pressure, heart rate was maintained within \pm 20% of the preoperative basic level. Correct acid-base imbalance and electrolyte disturbance according to arterial blood gas analysis.
- 7) analgesic connection: intravenous injection of 5mg oxycodone 30 minutes before the end of surgery.
- 8) At the end of the operation, the endotracheal tube was removed when the patient was awake. Measure the level of nerve block when the patient is conscious. If there was no nerve block plane, the patient was withdrawn from the trial. The patient-controlled intravenous analgesia, which equipped with 0.5mg/ml oxycodone, 1ml/h background infusion, 3ml additional infusion and locked for 5min, was used immediately after extubation.
- 9) The patients were observed in the PACU for one hour, and the PCA could be applied for additional analgesia according to the needs of the patients. The patient was given rescue analgesia, a single intravenous dose of 2 mg of oxycodone, if the pain was not relieved or the patient requested it. Patients took a sitting position and measured the VAS scores of the patients at rest and coughing at 1h postoperatively. FVC (L), FEV₁ (L) and FEF 25% -75% (L/sec) were measured by spirometer for three times., and three indexes of FVC (L), FEV₁ (L) and FEF 25% -75% (L/sec) were recorded by spirometer for three times. Ask the patient if there are any adverse reactions, such as nausea, vomiting, itching, dizziness, headache, shoulder pain, respiratory depression, etc.

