10) After returning to the ward, the patient can press the PCA for additional analgesia according to the needs. The patient was given rescue analgesia, a single use of diclofenac sodium suppository, if the pain was not relieved or the patient requested it. Investigators conducted postoperative visits at 2h, 4h, 8h and 24h postoperatively, the dosage of PCA, the times of rescue analgesia, VAS scores at rest and cough and adverse reactions were recorded. FVC (L), FEV1 (L) and FEF 25% -75% (L/sec) were recorded for three times by spirometer in the sitting position at 4h and 24h postoperatively. Patients were assessed postoperatively using the QoR-15 Patient Questionnaire at 24h postoperatively.

6. Outcome measurements

6.1 The primary outcome :

Cumulative morphine consumption at 24h postoperatively

6.2 The secondary outcomes:

- (1) The cumulative morphine consumption at 1h, 2h, 4h and 8h postoperatively.
- (2) The times of remedial analgesia at 1h, 2h, 4h, 8h and 24h postoperatively.
- (3) VAS score at rest and cough at 1h, 2h, 4h, 8h and 24h postoperatively.
- (4) The changes of FVC (L), FEV₁ (L) and FEF 25% - 75% (L / sec) were observed before operation, 1h, 4h and 24h after postoperatively.
- (5) Changes of QoR-15 questionnaire scores before and 24h postoperatively.
- (6) Postoperative complications and rehabilitation time nodes (including drainage tube removal time, discharge time, etc.).

7 Security

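### Serial secondary outcomes are assigned to one-way ANOVA with no stated factor, within-patient term or group-by-time term; the test and sidedness for the 24 h primary also need to be fixed

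*Combined protocol and SAP*

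**What the plan says.** Section 10 is the whole analysis plan and has two rules for continuous outcomes.

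- General rule: "Measurement data were analyzed and compared by t-test or Mann-Whitney U test, depending on whether the data were distributed normally or not".
- Rule for serial data: "Repeated measures data (e.g., morphine consumption, VAS scores, pulmonary function measures) were analyzed using one-way analysis of variance(ANOVA".

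The threshold is p < 0.05, with no sidedness given.

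Section 6.2 shows which outcomes are serial:

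- opioid use: "The cumulative morphine consumption at 1h, 2h, 4h and 8h postoperatively";
- pain: "VAS score at rest and cough at 1h, 2h, 4h, 8h and 24h postoperatively";
- spirometry: the changes of FVC, FEV1 and FEF 25-75%, which "were observed before operation, 1h, 4h and 24h after postoperatively".

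Section 6.1 gives the primary as "Cumulative morphine consumption at 24h postoperatively", one value per patient. Section 3.2 sizes the trial on that value, with a one-sided 5% test and 80% power. Section 11 adds: "Unblinding is performed when the statistical analysis is completed and the statistical analysis report is written by the statistical analyst".

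**The concern.** One-way ANOVA has one factor and assumes independent observations. Values from the same patient at 1, 2, 4, 8 and 24 h are not independent. The plan calls them repeated measures but provides nothing to handle the repetition. It also leaves the single factor unnamed, so analysts following the sentence could run materially different analyses. The results affected are the secondary ones on pain, lung function and early opioid use.

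A smaller issue concerns the primary. Morphine consumption is an example in the ANOVA sentence, while 24 h morphine as a single measurement falls under the t-test/Mann-Whitney rule. Neither rule states whether the test is one-sided, as the sample size assumes.

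**Working it through.** **1. The plan's own figure.** Inputs from section 3.2: difference 2.5 mg, pilot SDs 4.8 and 4.2 mg, one-sided 5%, power 80%, dropout 10%.

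- Pooled SD = √((4.8² + 4.2²)/2) = 4.51.
- n = 2(1.645 + 0.842)² × 4.51²/2.5² = 40.2, so 41 per arm.
- 82/0.9 = 91.1, so 92 in total.

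The stated figures reproduce. They describe a two-group comparison of means at one time.

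**2. Stacked times, groups compared.** Assumptions not in the documents: equal variances, common within-patient correlation ρ from 0.3 to 0.9, no group effect. With k times, the actual error of a nominal 5% test is about 2[1 − Φ(1.96/√R)], where R = (1 + (k−1)ρ)/(1 + v). Here v is the variance of the time means in SD² units, because an unmodelled time trend goes into the error term.

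| Setting | ρ = 0.3 | 0.5 | 0.7 | 0.9 |
|---|---|---|---|---|
| k = 5 (VAS), flat means | 18.6% | 25.8% | 31.5% | 36.1% |
| k = 4 (spirometry), flat means | 15.5% | 21.5% | 26.6% | 30.8% |
| k = 5, change of 3 SD over the visits | 5.4% | 9.9% | 14.3% | 18.3% |
| k = 5, change of 5 SD over the visits | 0.7% | 2.2% | 4.1% | 6.3% |

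For a change of d SD in equal steps over five visits, v = d²/8. The error exceeds 5% only while v < 4ρ, that is d < √(32ρ) = 3.1, 4.0, 4.7 or 5.4 SD. Simulation with 41 per arm agrees with the table, and a test on patient means returns to about 5%.

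Cumulative morphine cannot be flat, since the pump delivers "0.5mg/ml oxycodone, 1ml/h background infusion, 3ml additional infusion and locked for 5min", a background of at least 0.5 mg of oxycodone per hour. Take a mean of (23.7 + 28.7)/2 = 26.2 mg and SD 4.51 at 24 h, and assume variance proportional to time with independent increments. For the values at 1, 2, 4 and 8 h:

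- numerator of R = (37/4) × 4.51²/24 = 7.84;
- mean variance = 3.75 × 4.51²/24 = 3.18;
- variance of the time means under linear accrual = 7.19 × (26.2/24)² = 8.57;
- R = 7.84/(3.18 + 8.57) = 0.67, so the error is 1.6%.

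If only the background accrues (counted 1:1 as morphine, an assumption), the time term is 7.19 × 0.5² = 1.80, R = 1.58 and the error is 12%. The direction is therefore not fixed.

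**3. Time as the only factor.** Whether run within an arm or as a one-way repeated-measures ANOVA, the treatments are not compared.

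**4. Groups compared at each time.** Each test holds 5%. The chance of at least one false positive over five times is 10-21% for ρ from 0.9 down to 0.3 (simulated).

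**5. Groups compared on change from the preoperative spirometry value.** This is valid: simulated error was 5.0% and 5.3% at ρ = 0.5 and 0.7. For efficiency, take the mean of the three postoperative values, an assumed true effect of 0.5 SD, 41 per arm and a two-sided 5% test. In SD² units, with m = (1 + 2ρ)/3:

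- variance of change = m + 1 − 2ρ;
- variance after baseline adjustment = m − ρ².

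| ρ | Variance, change | Power | Variance, adjusted | Power |
|---|---|---|---|---|
| 0.5 | 0.667 | 0.78 | 0.417 | 0.93 |
| 0.7 | 0.400 | 0.94 | 0.310 | 0.98 |
| 0.9 | 0.133 | 1.00 | 0.123 | 1.00 |

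**6. The primary.** For two groups F = t², so one-way ANOVA and the two-sided equal-variance t-test give the same p-value. At 41 per arm the noncentrality is 2.5/(4.51√(2/41)) = 2.51. Power by noncentral t is 80.1% one-sided and 69.8% two-sided (76% to 64% for SD 4.2 to 4.8). Two-sided 80% needs 53 per arm (52 by the normal approximation).

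**The case against.** The strongest reply is that the sentence can be read in a valid way. Section 6.2 lists outcomes by time point, which suggests a test at each one. Its spirometry item speaks of changes, which suggests change from the preoperative value. Both analyses hold 5% per test, and the second does compare change between treatments. No section makes group-by-time an objective, and the multiplicity question would be the same with t-tests. All of this stands. A reader might infer that no reading compares the treatments over time, or that the secondary results carry a 19-36% error rate. The documents support neither: the large figures belong to a stacked analysis that no section describes, and they rest on assumed correlations and flat means.

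On the primary, section 6.1 separates 24 h morphine from the series in 6.2, so the t-test/Mann-Whitney rule is its natural home. A reader might infer that the ANOVA sentence inflates the primary or causes the fall in power to 70%. It does neither: a two-sided t-test loses the same power, so the cause is sidedness. Placing unblinding after the analysis also limits a result-driven choice of test.

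What remains is that the text does not choose among these readings. Some are invalid or do not compare the groups, and the valid ones do not analyse the times jointly.

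**Conclusion.** The concern holds as a defect of specification in the serial secondary outcomes. The one-way ANOVA sentence names no factor and has no within-patient or group-by-time term. Its effect ranges from a wrong error rate in either direction (stacked), through no treatment comparison (time as factor), to valid but separate tests (per time point or change score). For spirometry, change scores cost power at moderate correlation: 0.78 against 0.93 at ρ = 0.5, with little difference at 0.9. Every figure for the serial outcomes depends on assumed correlations, trends and effects, because the documents give none.

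For the primary, the wording blurs which rule applies, but no inflation is shown. The sidedness gap is a separate matter: 80% power at 2.5 mg and SD 4.51 holds only for the one-sided test of section 3.2.

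**What to change.** In section 10:

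- Replace one-way ANOVA for the serial secondary outcomes with a linear mixed model containing group, time and group-by-time, with an unstructured or otherwise suitable within-patient covariance. GEE with robust errors is acceptable. Two-factor repeated-measures ANOVA is acceptable only with a sphericity correction: with variance growing with time as assumed above for morphine, the uncorrected group-by-time test rejects 6-8% under the null.
- For spirometry, use the preoperative value as a covariate and the 1, 4 and 24 h values as outcomes.
- Report group differences at each time with 95% confidence intervals, either adjusted for multiplicity or labelled secondary and unadjusted.
- Limit the repeated-measures sentence to the serial secondary outcomes. Name one two-sample test for 24 h morphine and state its sidedness consistently with section 3.2. If it is to be two-sided, restate the power as about 70%.

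The cost is one rewritten paragraph and slightly more analysis work. No new data, visits or patients are needed. Only a decision to keep 80% power with a two-sided primary would raise the number, to about 53 per arm before dropout.
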